10.7.6.3 Use of Erythropoiesis-stimulating Agents

Background and Overview

ESAs are not approved in Japan for chemotherapy-induced anemia and the Sponsor considers that ESA use for belzutifan-induced anemia is off-label use in Japan.

CCI

Study Interventions Administered

In addition to the study intervention described in Table 2, the study intervention to be used in this study specific for Japan is outlined in Table 18.

Arm	Arm	Intervention	Туре	Dose	Unit Dose	Dosage	Route of	Regimen/	Use	IMP or	Sourcing
Name	Type	Name		Formu- lation	Strength(s)	Level(s)	Adminis- tration	Treatment Period		NIMP/ AxMP	
Belzut	Experi-	M-darbe	Combination	Sterile	180 μg	360 µg	SC	Refer to	Test	IMP	Central
llan	mental		Product	Solution	syringe			for	Product		
								belzutifan-			
								induced			
								anemia			
Abbreviations: EEA = European economic area; IMP = Investigational Medicinal Product; M-darbe = darbepoetin alfa; NIMP/AxMP = Noninvestigational/Auxiliary Medicinal											
Product; $SC =$ subcutaneously.											
According to hemoglobin level, dosage levels is to be reduced as outlined in the ESA dose for belzutifan-induced anemia.											
The participants who are assigned to the belzutifan arm will be administered M-darbe according to hemoglobin level.											
M-darbe will be provided as a single-dose prefilled syringe, which is defined as a combination product (syringe device and M-darbe).											
Note: The classification of IMP and NIMP/AxMP in this table is based on guidance issued by the European Commission and applies to countries in the EEA. Country											
differences with respect to the definition/classification of IMP and NIMP/AxMP may exist. In these circumstances, local legislation is followed.											

Table 18Study Interventions

Evaluation of M-darbe for Belzutifan-induced Anemia in Japanese Participants

All Japanese participants, including the participants in the safety run-in cohort, who receive at least 1 dose of belzutifan and receive at least 1 dose of M-darbe after experiencing belzutifan-induced anemia (hemoglobin <10.0 g/dL), will be evaluated to assess the effectiveness of M-darbe in the treatment of belzutifan-induced anemia. The following endpoints will be evaluated and reported for Japanese participants:

• Percentage of participants with change from baseline in hemoglobin $\geq 2.0 \text{ g/dL}$

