Percentage of participants with change from baseline in hemoglobin ≥ 2.0 g/dL will be calculated. Baseline measurement is defined as the last value measured between start date of the AE of anemia and before the first M-darbe administration for each participant. The postbaseline measurements are defined as the values measured after the start date of receiving M-darbe, and before the earliest date of 12 weeks after receiving M-darbe, the date of discontinuation of belzutifan, and the start date of blood transfusion. Change from baseline in hemoglobin will be calculated as the maximum value of postbaseline measurements minus the value of baseline measurement.

• Percentage of avoidance of a blood transfusion

Percentage of avoidance of a blood transfusion will be calculated and is defined as the percentage of participants who did not receive a blood transfusion.

- The percentage of participants whose minimum value of post-baseline measurements of hemoglobin ≥7.0 g/dL
- The percentage of participants whose minimum value of post-baseline measurements of hemoglobin ≥8.0 g/dL

In addition, AEs will also be summarized for all participants included in this evaluation of M-darbe.

AE Monitoring and Reporting Related to M-darbe

Based on Sections 1.3 and 8.4, AE monitoring of administration of M-darbe, which is considered as an IMP in Japan, will also be performed. Treatment with M-darbe is considered as study intervention, and therefore, the time period for collecting AE, SAE, and other reportable safety event information will be as described in Section 8.4.1.

Concomitant Therapy

Based on Section 6.5, all concomitant medications received within 28 days before randomization and up to 30 days after the last dose of study intervention, defined by the last dose of belzutifan, everolimus, or M-darbe should be recorded. Concomitant medications administered >30 days after the last dose of study intervention defined by the last dose of belzutifan, everolimus, or M-darbe should be recorded for SAEs as defined in Section 8.4.

Serious Syringe Device Events (Incidents)

M-darbe will be provided as a single-dose prefilled syringe, which is defined as a combination product (syringe device and M-darbe). A syringe device corresponds to a medical device, and serious syringe device events (incidents) must be reported to the Sponsor.

Instructions for medical device use are provided in the Pharmacy Manual.

Definition of Serious Syringe Device Events (Incidents)

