10.8.2 Anemia/Decreased Hemoglobin ECI Reporting

The following AE terms are considered ECIs and should be reported to the Sponsor within 5 calendar days of learning of the event if the event is non-serious or within 24 hours if the event is an SAE:

- ≥Grade 3 anemia
- *Erade 3 decreased hemoglobin*

Definition: A disorder characterized by a reduction in the amount of hemoglobin in 100 mL of blood. Signs and symptoms of anemia may include pallor of the skin and mucous membranes, shortness of breath, palpitations of the heart, soft systolic murmurs, lethargy, and fatigability.

CTCAE Version 5 definition of Anemia Grades:

- Grade 1: Hemoglobin <LLN 10.0 g/dL; <LLN 6.2 mmol/L; <LLN 100 g/L
- Grade 2: Hemoglobin <10.0 8.0 g/dL; <6.2 4.9 mmol/L; <100 80 g/L
- Grade 3: Hemoglobin <8.0 g/dL; <4.9 mmol/L; <80 g/L; transfusion indicated
- Grade 4: Life-threatening consequences; urgent intervention indicated
- Grade 5: Death

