10.8.3 Anemia Management

Decreased EPO is the potential etiology of anemia with belzutifan treatment. EPO replacement is an effective management strategy for participants who may develop and subsequently require intervention for belzutifan-induced anemia. Transfusion can also be used to manage anemia in patients receiving belzutifan.

155

Grade 3 events (report as ECI):

• Dose Modification not required

Grade 4 events (report as ECI):

- First episode: Hold belzutifan. Once toxicity has resolved to ≤Grade 2 or baseline, dose reduce belzutifan by 1 level
- Second episode: Permanently discontinue belzutifan

All attempts should be made to rule out other causes of anemia. Relevant diagnostic studies may include peripheral blood smear, reticulocyte count, LDH, haptoglobin, Coomb's test, blood levels of vitamin B12, folate, iron studies, etc.

While dose interruption is not required, the investigator may elect to hold belzutifan for participants who develop anemia Grade 1-3. If belzutifan is held for anemia Grade 1-3, the participant can be re-challenged with belzutifan at the same dose.

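### The two Japan M-darbe minimum-hemoglobin endpoints drop values drawn on the day of transfusion or belzutifan discontinuation, which can overstate the rates

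*Protocol*

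**What the plan says.** Protocol Section 10.7.6.3 lists four percentages for Japanese participants who had belzutifan-induced anemia and received at least one dose of M-darbe: a hemoglobin rise of at least 2.0 g/dL, avoidance of transfusion, and a minimum hemoglobin at or above each of two thresholds.

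The measurement window is defined once, under the rise endpoint. It opens as follows: "The postbaseline measurements are defined as the values measured after the start date of receiving M-darbe". It closes "before the earliest date of 12 weeks after receiving M-darbe, the date of discontinuation of belzutifan, and the start date of blood transfusion".

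The two minimum endpoints are "The percentage of participants whose minimum value of post-baseline measurements of hemoglobin ≥7.0 g/dL" and "The percentage of participants whose minimum value of post-baseline measurements of hemoglobin ≥8.0 g/dL". Both rely on that window. The visible text gives them no other, and the supplemental SAP (Section 3.6.5 covers the Japan run-in cohort) does not mention them.

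Transfusion enters as an outcome only in the avoidance percentage, "defined as the percentage of participants who did not receive a blood transfusion", which carries no time limit.

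The only hemoglobin level that the visible text links to transfusion is in the CTCAE grading in Section 10.8.2: "Grade 3: Hemoglobin <8.0 g/dL; <4.9 mmol/L; <80 g/L; transfusion indicated". Section 10.8.3 adds: "Transfusion can also be used to manage anemia in patients receiving belzutifan".

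**The concern.** The rise endpoint takes a maximum. Stopping at transfusion keeps donor blood from being credited to M-darbe, so the cut is sensible there. The two later endpoints take a minimum. Removing values from a set can never lower its minimum, so the same cut works in one direction only, and it falls where a low value is most likely: the day someone decided to transfuse.

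The evaluation is meant to judge whether M-darbe is effective, and everyone in it receives M-darbe. No comparison group would carry the same error and so reveal it.

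**Working it through.** The documents give no sample size, expected rate or transfusion frequency for these endpoints, so there is no plan figure to reproduce. I applied the window literally and then sized the effect under assumptions.

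**Step 1. Scoring rule.** A value counts if M-darbe start < date < min(12 weeks, belzutifan discontinuation, transfusion start). The endpoint is met if the smallest counted value is at or above the threshold. M-darbe starts on day 0. In every case except the fourth, hemoglobin on day 14 is 8.9 g/dL.

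| Hypothetical history | ≥7.0 | ≥8.0 | Comment |
|---|---|---|---|
| 6.8 on day 27, transfused day 28 | not met | not met | correct |
| 6.8 on day 28, transfused day 28 | met | met | wrong on both; the 6.8 is dropped |
| 7.5 on day 28, transfused day 28 | met | met | ≥7.0 correct, ≥8.0 wrong |
| Only value 6.8 on day 14, transfused day 14 | no value | no value | no rule stated |
| 7.5 on day 27, transfused day 28 | met | not met | correct |
| 8.4 on day 27, transfused day 28 | met | met | correct on measured values |
| Belzutifan stopped day 20, 6.8 on day 28 | met | met | later fall cut off |

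The clear errors are the histories in which the low value and the transfusion share a date. A low value on the discontinuation date is lost in the same way.

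**Step 2. Size by hand (assumed figures).** Take 20 participants: 14 meet the criterion, and 6 are transfused after a value below the threshold. Let f be the share of those 6 whose low value falls on the transfusion date, each with an earlier passing value.

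Rate as written = (14 + 6f)/20. Rate with same-day values kept = 14/20 = 70%.

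- f = 0: 70%
- f = 0.25: 77.5%
- f = 0.5: 85%
- f = 1: 100%

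The overstatement is 6f/20, proportional to f.

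**Step 3. Size by simulation (assumed figures).** Baseline hemoglobin 8.0-9.9 g/dL; mean drift zero with SD 0.12 g/dL per week; measurement SD 0.4 g/dL; a value every 2 or 4 weeks to week 12; each value below 8.0 leads to transfusion with probability 0.9. Ranges cover the two visit intervals. The reference column counts a transfused participant as not meeting ≥8.0. In this model that equals keeping the same-day value, because every transfusion follows a value below 8.0.

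| Share of transfusions on the draw date | ≥8.0 as written | ≥8.0 reference |
|---|---|---|
| 100% | about 96% | 62-68% |
| 50% | 79-81% | 62-67% |
| 25% | 70-74% | 63-67% |
| 10% | 65-70% | 62-68% |
| 0% | same as reference | 62-68% |

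For ≥7.0 with all transfusions same-day, the rate as written is 99.6-99.8%. Restoring the dropped values gives 96.5-98.4%, a change of roughly 1 to 3 points. Counting any transfusion as failure gives about 63-69%, but that is a different endpoint.

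The model counts the week-12 value. Leaving it out, on a strict reading of the 12-week limit, narrows the ≥8.0 gap somewhat and does not change its direction.

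**The case against.** The fall comes before the transfusion. A reader might infer that anyone who drops to the transfusion level is scored as a success. The documents do not support that: any low value dated before the transfusion stays in the window and fails.

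Same-day transfusion may also be uncommon. The Schedule of Activities sends hematology to the central laboratory, which makes a same-day result less likely for scheduled samples. Appendix 2 allows for local results being used in treatment decisions, so same-day cases can occur, but no document says how often.

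For ≥7.0 the objection is stronger still. Someone transfused at 7.0-7.9 g/dL has met that criterion up to that point. Whether transfusion should count as failure is a choice of estimand, and transfusion is already reported in its own percentage beside these two.

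Discontinuation matters less: for anemia, Table 3 and Section 10.8.3 call for permanent discontinuation only with Grade 4 events. Parts of Section 10.7.6 are redacted and may hold Japan-specific rules.

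Most of this stands, and it limits the size of the problem. It does not remove the same-day error. The visible definition deletes a measured pre-transfusion value from a minimum. The avoidance percentage cannot restore that value, and it has no stated 12-week limit.

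**Conclusion.** The point holds in a limited form. For the two minimum-hemoglobin endpoints, the shared window drops a below-threshold value drawn on the date of transfusion or belzutifan discontinuation, and it cuts off later falls without counting them. Among participants with a value left in the window, this can only push the rates up.

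For ≥8.0 the overstatement rises with the share of transfusions given on the trigger date: nothing at zero, and about 96% against 62-68% only if all are same-day. Those figures rest on the assumed drift, variability, visit interval and 90% transfusion probability. For ≥7.0 the same correction moves the simulated rate by only a few points.

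A reader might go further and infer that both rates would sit near 100% whether or not M-darbe works. For ≥8.0 that needs nearly all transfusions to be same-day, which the documents do not establish. For ≥7.0 a high rate can simply be correct.

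The stakes are Japan-only descriptive percentages with no hypothesis test. PFS, OS, ORR and the alpha plan are unaffected.

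**What to change.** For the two minimum-hemoglobin endpoints only, include hemoglobin values dated on the day of transfusion or of belzutifan discontinuation. Keep the existing window for the ≥2.0 g/dL rise endpoint. Say how a participant with no value in the window is counted.

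As a supportive analysis, report each minimum rate again with participants transfused within the 12-week window counted as not meeting the criterion. Give the avoidance-of-transfusion rate over the same 12 weeks so that the figures cover one period.

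The cost is a few sentences. Hemoglobin is measured at each clinic visit (Section 6.6.1.1) and transfusions are recorded on the eCRF (Section 6.5), so no new data are needed. Protocol Section 9 allows changes to nonconfirmatory analyses to be documented in the supplemental SAP if made before the analysis is run. The downside is that the reported rates may be slightly less favourable. No clinical rule changes.

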10.7.7 South Korea

Section 5.1 Inclusion Criterion 11

System	Laboratory Value		
Hematological			
	>1500 cells/uI		
Platelets	≥ 100.000 cells/µL		
Hemoglobin	$\geq 100 000 \text{ cens/}\mu\text{L}$ $\geq 10.0 \text{ g/dL} \text{ or } \geq 6.2 \text{ mmol/}\text{L}$		
Renal			
Serum creatining or estimated CrCl using the	<1.5 × ULNOR		
Cockcroft-Gault equation or based on a 24-hour	>51 mL/min for participants with creatining levels		
urine test ^a (GFR can also be used in place of	\geq 51 mL/mm for participants with creatinine revers		
creatinine or CrCl)			
Henatic			
Total hilimhin	<1.5 × ULN OR direct bilirubin <uln for<="" td=""></uln>		
	participants with total bilirubin levels $>1.5 \times ULN$		
AST (SGOT) and ALT (SGPT)	$<2.5 \times \text{ULN}$ ($<5 \times \text{ULN}$ for participants with liver		
	metastases)		
Coagulation			
INR or PT, and aPTT	<1.5 × ULN unless participant is receiving		
	anticoagulant therapy as long as PT or aPTT is		
	within the apeutic range of intended use of		
	anticoagulants		
Fasting serum triglycerides and total cholesterol	\leq 2.5 x ULN AND total cholesterol \leq 300 mg/dL		
	$(\leq 7.75 \text{ mmol/L})$. Lipid-lowering medication is		
	allowed		
Fasting glucose	A fasting glucose $\leq 125 \text{ mg/dL}$ ($\leq 6.9 \text{ mmol/L}$) is		
	required.		
Abbreviations: ALT (SGPT)=alanine aminotransferase (serum glutamic-pyruvic transaminase); ANC=absolute			
neutrophil count; aPTT=activated partial thromboplastin time; AST (SGOT)=aspartate aminotransferase (serum			
glutamic-oxaloacetic transaminase); CrCl=creatinine clearance; GFR=glomerular filtration rate; INR=international			
normalized ratio; pRBC=packed red blood cells; PI=prothrombin time; ULN=upper limit of normal.			
a. Estimated creatinine creatance using Cockeront-Gaunt: $(140 \text{ age [veered]} \times \text{weight } (k_{c}) = (XF)^*$			
Serum creatining $(m\sigma/dL) \times 72$			
*where $F = 0.85$ for females and $F = 1$ for males			
Note: This table includes eligibility-defining laboratory value requirements for treatment; laboratory value requirements			
should be adapted according to local regulations and guidelines for the administration of specific chemotherapies.			

Table 19Adequate Organ Function Laboratory Values

10.8 Appendix 8: Belzutifan ECI Guidance

10.8.1 Belzutifan ECI Criteria

Anemia: Any ≥ Grade 3 anemia/decreased hemoglobin event				
Anemia Decreased hemoglobin				
Hypoxia: Any ≥ Grade 3 hypoxia				
Нурохіа				
Any ≥Grade 3 SAE/AE deemed related to belzutifan by the investigator, including laboratory				
abnormalities.				
\geq Grade 3 belzutifan-related clinical AEs \geq Grade 3 belzutifan-related laboratory AEs				
Common Terminology Criteria for Adverse Events (CTCAE) Version 5 will be used.				

10.8.2 Anemia/Decreased Hemoglobin ECI Reporting

The following AE terms are considered ECIs and should be reported to the Sponsor within 5 calendar days of learning of the event if the event is non-serious or within 24 hours if the event is an SAE:

- ≥Grade 3 anemia
- *Erade 3 decreased hemoglobin*

Definition: A disorder characterized by a reduction in the amount of hemoglobin in 100 mL of blood. Signs and symptoms of anemia may include pallor of the skin and mucous membranes, shortness of breath, palpitations of the heart, soft systolic murmurs, lethargy, and fatigability.

CTCAE Version 5 definition of Anemia Grades:

- Grade 1: Hemoglobin <LLN 10.0 g/dL; <LLN 6.2 mmol/L; <LLN 100 g/L
- Grade 2: Hemoglobin <10.0 8.0 g/dL; <6.2 4.9 mmol/L; <100 80 g/L
- Grade 3: Hemoglobin <8.0 g/dL; <4.9 mmol/L; <80 g/L; transfusion indicated
- Grade 4: Life-threatening consequences; urgent intervention indicated
- Grade 5: Death

10.8.3 Anemia Management

Decreased EPO is the potential etiology of anemia with belzutifan treatment. EPO replacement is an effective management strategy for participants who may develop and subsequently require intervention for belzutifan-induced anemia. Transfusion can also be used to manage anemia in patients receiving belzutifan.

155

Grade 3 events (report as ECI):

• Dose Modification not required

Grade 4 events (report as ECI):

- First episode: Hold belzutifan. Once toxicity has resolved to ≤Grade 2 or baseline, dose reduce belzutifan by 1 level
- Second episode: Permanently discontinue belzutifan

All attempts should be made to rule out other causes of anemia. Relevant diagnostic studies may include peripheral blood smear, reticulocyte count, LDH, haptoglobin, Coomb's test, blood levels of vitamin B12, folate, iron studies, etc.

While dose interruption is not required, the investigator may elect to hold belzutifan for participants who develop anemia Grade 1-3. If belzutifan is held for anemia Grade 1-3, the participant can be re-challenged with belzutifan at the same dose.

10.8.4 Hypoxia ECI Reporting

The following AE terms are considered ECIs and should be reported to the Sponsor within 5 calendar days of learning of the event if the event is non-serious or within 24 hours if the event is an SAE:

• \geq Grade 3 hypoxia

Definition: A disorder characterized by a decrease in the level of oxygen in the body.

CTCAE Version 5 definition of Hypoxia Grades:

- Grade 1: Not Applicable
- Grade 2: Decreased oxygen saturation with exercise (eg, pulse oximeter <88%); intermittent supplemental oxygen
- Grade 3: Decreased oxygen saturation at rest (eg, pulse oximeter <88% or PaO2 <=55 mm Hg)
- Grade 4: Life-threatening airway compromise; urgent intervention indicated (eg, tracheotomy or intubation)
- Grade 5: Death

[National Cancer Institute 2017]

10.8.5 Hypoxia Management

Grade 3 events (report as ECI):

- Consult pulmonology
- Provide supplemental oxygen
- Consider appropriate clinical work-up including chest x-ray/CT and ECG to evaluate for potential concomitant/underlying etiologies
- First and second episodes: Hold belzutifan. Once toxicity has resolved to ≤Grade 2 or baseline, dose reduce belzutifan by 1 level (Grade 3 hypoxia [asymptomatic], belzutifan may be continued at the discretion of the investigator)
- Third episode: Permanently discontinue belzutifan

Grade 4 events (report as ECI):

- Consult pulmonology
- Provide supplemental oxygen and endotracheal intubation if indicated
- Consider appropriate clinical work-up including chest x-ray/CT and ECG to evaluate for potential concomitant/underlying etiologies
- Permanently discontinue belzutifan

All attempts should be made to characterize the etiology of the events associated with hypoxia such as heart disease, pulmonary infection, pulmonary metastasis, chronic obstructive pulmonary disease, interstitial lung disease, pulmonary embolism, acute respiratory distress syndrome, chronic liver disease, etc.

10.9 Appendix 9: Abbreviations

Abbreviation	Definition
ADME	Absorption, distribution, metabolism, and excretion
AE	Adverse event
AEOSI	Adverse events of special interest
ALP	Alkaline phosphatase
ALT	Alanine aminotransferase
ANC	Absolute neutrophil count
APaT	All-Participants-as-Treated
aPTT	Activated partial thromboplastin time
ARNT	Aryl hydrocarbon receptor nuclear translocator
AST	Aspartate aminotransferase
AUC	Area under the curve
BCG	Bacillus Calmette–Guérin
BCRP	Breast cancer resistance protein
BCS	Biopharmaceutics Classification System
β-hCG	β-human chorionic gonadotropin
BICR	Blinded independent central review
BID	Twice daily
BUN	Blood urea nitrogen
Ca	Calcium
CBC	Complete blood count
ccRCC	Clear cell renal cell carcinoma
CI	Confidence interval
Cl	Chloride
cLDA	Constrained longitudinal data analysis
CL/F	Clearance
C _{max}	Maximum concentration
CNS	Central nervous system
CO ₂	Carbon dioxide
CONSORT	Consolidated Standards of Reporting Trials
CR	Complete response
CrCl	Creatinine clearance
CRF	Case Report Form
CSR	Clinical Study Report
	Computed tomography
CICAE	Common Terminology Criteria for Adverse Events
CIFG	Clinical Irial Facilitation Group
CV	Vonichility
	Valiability
D	Cytochionic P450
ע מפת	Diestalie blood pressure
DC	Discontinuation
	Dese limiting toxicity
DLI	Dote Monitoring Committee
DNA	Deavyribonucleic acid
DOR	Duration of response
DU	Current dose is unaccentably toxic
F	Escalate to the next higher dose
E	Electrocardiogram

Abbreviation	Definition
ECI	Event of clinical interest
eCRF	Electronic Case Report Form
ECOG	Eastern Cooperative Oncology Group
EDC	Electronic data collection
ELISA	Enzyme-linked immunosorbent assay
EOC	Executive Oversight Committee
EORTC OLO-C30	European Organisation for the Research and Treatment of Cancer Quality of Life
	Questionnaire 30
EOT	End-of-treatment
EPO	Erythropoietin
ESA	Erythropoiesis-stimulating agents
ESMO	European Society for medical Oncology
EuroOoL EO-5D-	European Quality of Life (EuroOoL)-5 dimensions-5 levels
5L	
Exp	Experimental
FA	Final analysis
FAS	Full Analysis Set
FBR	Future biomedical research
FDAAA	Food and Drug Administration Amendments Act
FFPF	Formalin-fixed paraffin embedded
FKSLDRS	Functional Assessment of Cancer Therapy – Kidney Symptom Index-disease-related
I KSI DIG	symptoms
FSH	Follicle-stimulating hormone
GCP	Good Clinical Practice
G-CSF	Granulocyte Colony-Stimulating Factor
GER	Glomerular filtration rate
GLP	Good Laboratory Practice
GM-CSF	Granulocyte Macronhage Colony-Stimulating Factor
НА	Health authority
HBsAg	Henatitis B surface antigen
HBV	Henatitis B virus
HCV	Henatitis C virus
HDPF	High-density polyethylene
HIF 1R	Hypoxia inducible factor 18
HIF 2a	Hypoxia inducible factor 2g
HIV	Human immunodeficiency virus
HP	Hazard ratio
HROOL	Health related quality of life
HRT	Hormone replacement therapy
	Interim analysis
IR	Investigator's Brochure
IC	Half maximal inhibitary concentration
IC50	Informed Consent Form
	International Council on Harmonisation
ICMIE	International Committee of Medical Journal Editors
iCRO	Imaging contract research organization
ID	Identification
IEC	Independent Ethics Committee
IHC	Immunohistochemistry
IMDC	International Metastatic Renal Cell Carcinoma Database Consortium
IMP	Investigational Medicinal Product
IND	Investigational New Drug
IND	International normalized ratio
11 / 17	

159

Abbreviation	Definition
IRB	Institutional Review Board
IRT	Interactive response technology
ITT	Intent-to-treat
IUD	Intrauterine device
IUS	Intrauterine hormone-releasing system
IV	Intravenous(1y)
IVD	In vitro diagnostic
К	Potassium
KPS	Karnofsky performance status
LAM	Lactational amenorrhea method
LLN	Lower limit of normal
M-darbe	NESP; darbepoetin alfa
Mg	Magnesium
MRI	Magnetic resonance imaging
mRNA	Messenger RNA
MTD	Maximum tolerated dose
mTPI	Modified toxicity probability interval
Na	Sodium
NCCN	The National Comprehensive Cancer Network
NCI	National Cancer Institute
NIMP	Non-investigational Medicinal Product
OR	Objective response
ORR	Objective response rate
OS	Overall survival
OTC	Over-the-counter
PAS	Per-ARNT-Sim
PD-1	Programmed cell death 1
PD-L1	Programmed cell death 1 ligand 1
pEFD	Preliminary embryo-fetal toxicity
PFS	Progression-free survival
P-gp	P-glycoprotein
РК	Pharmacokinetic
PO4	Phosphate
PR	Partial response
pRBC	Packed red blood cells
PRO	Patient-reported outcome
PT	Prothrombin time
Q3W	Every 3 weeks
Q4W	Every 4 weeks
Q8W	Every 8 weeks
Q12W	Every 12 weeks
Q16W	Every 16 weeks
Q24W	Every 24 weeks
QD	Once daily
QoL	Quality of life
RBC	Red blood cell
RCC	Renal cell carcinoma
RECIST	Response Evaluation Criteria in Solid Tumors
RNA	Ribonucleic acid
S	Stay at the current dose
SAC	Scientific Advisory Committee
SAE	Serious adverse event

Abbreviation	Definition
SBP	Systolic blood pressure
SC	Subcutaneously
SD	Stable disease
SIM	Site Imaging Manual
SLC2A1	Solute carrier family 2 member 1
SoA	Schedule of activities
SOC	System organ class
sSAP	Supplemental Statistical Analysis Plan
SUSAR	Suspected unexpected serious adverse reaction
TB	Bacillus tuberculosis
TK	Toxicokinetic
TKI	Tyrosine kinase inhibitor
t _{max}	Time to maximum concentration
TTD	Time to deterioration
UGT	Uridine 5'-diphospho-glucuronosyltrasnferase
ULN	Upper limit of normal
VAS	Visual Analog Scale
VEGF	Vascular endothelial growth factor
VEGF-A	Vascular endothelial growth factor-A
VHL	Von Hippel Lindau
VZ/F	Apparent volume of distribution
WBC	White blood cell
Wk	Week
WOCBP	Woman/women of childbearing potential

